5.4 PARTICIPANT WITHDRAWAL OR TERMINATION

5.4.1 REASONS FOR WITHDRAWAL OR TERMINATION

- Active (voluntary) withdrawal of consent by the study participant
- Transfer of care to a non-participating dialysis clinic
- An investigator may terminate participation in the study if:
 - Non-adherence to study data collection procedures (refusal of TTE, blood draw or symptom monitoring)
 - Violation of the inclusion/ exclusion criteria determined after the fact
 - Any clinical AE, laboratory abnormality or other medical condition or situation occurs such that continued participation in the study would not be in the best interest of the participant

5.4.2 HANDLING OF PARTICIPANT WITHDRAWALS OR TERMINATION

While participants will be encouraged to complete the study, they may withdraw from the study at any time and for any reason. Every effort will be made to determine why any participant withdraws from the study prematurely. This information will be recorded. Withdrawn subjects will be replaced, until 30 participants complete the study.

5.5 PREMATURE TERMINATION OR SUSPENSION OF STUDY

If the investigators becomes aware of conditions or events that suggest a possible hazard to subjects if the clinical study continues, the clinical study may be terminated after appropriate consultation between the involved parties. Conditions that may warrant termination of the clinical study include, but are not limited to: the discovery of an unexpected, relevant or unacceptable risk to the participants enrolled in the clinical study or failure to enroll participants at the required rate.

6 STUDY AGENT/ INTERVENTION

6.1 STUDY INTERVENTION AND CONTROL DESCRIPTION

6.1.1 DESCRIPTION

Intervention (UF profile during HD): The study intervention arm is linear UF profiling (linearly decreasing UF rate with a UF rate starting at 1.33 times the rate that would be needed at a constant UF rate to achieve the desired post-weight; pre-programmed “profile 2” on a Fresenius 2008K machine, the machine used in all participating clinics).

Routine care/ control (conventional HD): The study control arm is conventional HD (the patient’s standard HD prescription without UF profiling).

6.1.2 DURATION OF THERAPY

Patients will undergo 9 treatments during each phase for a total of 18 conventional HD treatments and 18 UF profiled treatments. Patients will undergo 3 wash-out HD treatments between phases. There will be a total of 45 study treatments (36 study treatments and 9 washout treatments). The baseline study visit will involve a history and physical and baseline transthoracic echocardiography study. The entire study duration for each individual is 16 weeks (15 treatments and 1 baseline study visit).

6.2 STUDY AGENT ACCOUNTABILITY PROCEDURES

N/A

7 STUDY PROCEDURES AND SCHEDULE

7.1 STUDY PROCEDURES/EVALUATIONS

7.1.1 STUDY SPECIFIC PROCEDURES

UF profiled HD treatments (intervention): The study treatments will be administered at routine, scheduled outpatient thrice-weekly HD clinic visits. Dialysis clinic nursing staff will select UF profile 2 on the dialysis machine at the start of each UF profiled treatment. Clinic nursing staff have experience using UF profiling as it is a standard HD machine setting. Dialysate composition and HD medications will be per baseline prescription determined by the treating nephrologist. Total UF volume and target weight will be determined by the treating nephrologist.

Medical history: At baseline, the participant’s medical history will be taken from the electronic medical record and confirmed verbally with the patient. The medical history will include a review of co-morbid conditions, medications

and performance of a physical examination (Vital signs- BP, heart rate, respiratory rate, weight, height; systems- cardiovascular, pulmonary, neurological)

7.1.2 STANDARD OF CARE STUDY PROCEDURES

Standard HD treatments without UF profiling (control): Fresenius 2008K HD machines, a dialysate temperature of 37°C, and patients' standard blood and dialysate flows will be used. No sodium profiling will be used. Dialysate composition and HD medications will be per baseline prescription determined by the treating nephrologist. Total UF volume and target weight will be determined by the treating nephrologist.

Standard-of-care BP measurement: BPs will be machine-measured with an upper extremity cuff in the seated position pre- and post-dialysis and every 20 minutes during every dialysis treatment.

Standard-of-care weight measurement: Per routine practice, target weight will be estimated by the treating nephrologist. Pre- and post-dialysis weights will be measured before and after each treatment in the standing position.

7.2 LABORATORY PROCEDURES/EVALUATIONS

7.2.1 CLINICAL LABORATORY EVALUATIONS

Troponin T (blood sample): Blood samples for Troponin T measurement will be collected via the vascular access by dialysis clinic staff. Troponin T will be collected before and after the 7th HD treatment of each phase for the calculation of troponin T change (2 troponin T changes during UF profiled HD and 2 during control HD). Troponin T is the only laboratory test to be performed as part of the study.

Standard-of-care laboratory measurements: Study start will be timed so that standard-of-care monthly lab testing (electrolytes, albumin, complete blood count, Kt/V, iron stores, bone-mineral tests) will be drawn within 6 weeks prior to study start (baseline). A 24-hour urine collection will be performed during baseline to measure residual kidney function (mL urine/day). These standard-of-care laboratory measurements will be performed as part of routine clinical care and are not study-specific.

7.2.2 OTHER ASSAYS OR PROCEDURES

TTE: Patients will undergo intradialytic TTE at baseline (within 6 weeks prior to study start) and 30 minutes prior to HD end ("peak stress") during treatment 7 of the first phase of each treatment type (once during conventional and once during UF profiled treatment) (1 TTE during UF profiled HD and 1 during control HD). Study TTEs will be performed by a trained sonographer with a Philips CX50 ultrasound system (Philips North America).

Blood volume monitoring: Blood volume monitoring will be performed continuously throughout each study treatment via a Crit-line™ (standard-of-care non-invasive relative blood volume monitoring tool used as part of standard dialysis treatments).

Plasma refill test: Using the blood volume monitor, a plasma refill test will be performed 10 minutes before HD end during the 7th treatment of each phase. At the start of the treatment, UF time will be set 10 minutes less than treatment time. When the dialysis UF ends, study staff will document the hematocrit (%) from the blood volume monitor, and when the treatment ends, document the blood volume monitor hematocrit (%) again. Plasma refill tests are part of the blood volume monitoring protocols at the selected units and are familiar to staff.

Patient acceptance: At the end of the 9th study treatment of each phase, study staff will ask the participant the following question: "If recommended by your physician, would you be willing to adopt the HD prescription you have received during the last 9 treatments?"

Symptom assessment: At the conclusion of the 1st study treatment each week, study staff will ask patients to complete a symptom questionnaire (Appendix B).

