4 STUDY DESIGN AND ENDPOINTS

4.1 DESCRIPTION OF THE STUDY DESIGN

The study is a 4-period cross-over trial (see schematic of study design) in which participants are successively alternated between study arms across 4 periods with intervening washout periods, and treatment order is randomized. The study control arm is conventional HD: the patient's standard HD prescription (no UF profiling). The study experimental arm is conventional HD + linear UF profiling. Linear UF profiling will be specified as a linearly decreasing UF rate with a UF rate starting at 1.33 times the rate that would be needed at a constant UF rate to achieve the desired post-weight (Fresenius 2008K machine profile 2). After providing consent, patients will be randomly allocated to experimental or control treatment for period 1. Patients will undergo 9 treatments during each phase for a total of 18 conventional HD treatments and 18 UF profiled treatments. Patients will undergo 3 wash-out HD treatments between phases. The study will be double-blinded in that patients will not be informed of the treatment paradigm. Investigators, including those performing TTE interpretation, will be blinded to treatment paradigm. Ultrasonographers performing intra-HD TTEs will be blinded to treatment paradigm.

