4.2.2 SECONDARY ENDPOINTS

- 1) Systolic BP change: measured on a per-treatment basis; defined as pre-HD – nadir intra-HD systolic BP (mmHg)
- 2) Nadir systolic BP: measured on a per-treatment basis; defined as the minimum intradialytic systolic BP (mmHg)
- 3) Target weight achievement: measured on a per-treatment basis: defined as post-HD weight within 1 kg of prescribed target weight.
- 4) Weight difference: measured on a per-treatment basis; defined as target weight – post-HD weight (kg)
- 5) Patient acceptance: measured after treatment 9 of each phase; response to the following question, "If recommended by your physician, would you be willing to adopt the HD prescription you have received during the last 9 treatments?"

6) TTE ejection fraction (EF): measured 30 minutes before HD end during 7th treatment in the first phase of each treatment type (once during conventional and once during UF profiled treatment); defined as % EF change (baseline – intradialytic EF), see Appendix A for TTE protocol

7) Patient-reported symptoms: measured after the 1st HD treatment each week; see Appendix B for data collection form.

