9 CLINICAL MONITORING

Clinical site monitoring is conducted to ensure that the rights and well-being of human subjects are protected, that the reported trial data are accurate, complete, and verifiable, and that the conduct of the trial is in compliance with the currently approved protocol/ amendment(s) and with GCP. The PI and research Study Coordinator will conduct on-site monitoring (at least once per study phase) and centralized monitoring (every study treatment) for all study participants at all study sites to verify protocol adherence/ study conduct, data collection, and safety.

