10.4.3 ANALYSIS OF THE SECONDARY ENDPOINT(S)

Comparisons of values for the binary secondary endpoints of target weight achievement, patient acceptance, and symptom occurrence between HD treatments will be performed using generalized estimating equations. Comparisons of values for the continuous secondary endpoints of pre-HD to nadir intradialytic HD systolic BP change, intradialytic nadir systolic BP change, target and post-HD weight difference, and TTE ejection fraction change will be performed using ANOVA or non-parametric methods depending on data type.

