10.6 MEASURES TO MINIMIZE BIAS

10.6.1 ENROLLMENT/ RANDOMIZATION/ MASKING PROCEDURES

Randomization assignments will be generated using computer-generated random numbers. Assignments will be sealed in envelopes prior to study start. After patients consent to study participation, sealed study arm assignments will be randomly allocated to experimental or control treatment for period 1. Sequence assignments will be sealed in envelopes prior to study start and opened in a predetermined order at the start of each study period. The study will be double-blinded in that patients will not be informed of the treatment paradigm. Investigators, including those performing TTE interpretation, will be blinded to treatment paradigm. Ultrasonographers performing intra-HD TTEs will be blinded to treatment paradigm.

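### Patient acceptance is asked aloud by study staff whose masking is not stated; a self-completed form would take the asker out of a subjective secondary endpoint

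*Combined protocol and SAP*

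**What the plan says.** Section 4.2.2 of the protocol lists the endpoint: "Patient acceptance: measured after treatment 9 of each phase; response to the following question". Section 7.2.2 gives the method of collection: "At the end of the 9th study treatment of each phase, study staff will ask the participant the following question". The next paragraph of 7.2.2 handles the other patient-reported outcome differently: patients complete the symptom questionnaire in Appendix B themselves. Section 10.4.3 says that comparisons for the "binary secondary endpoints of target weight achievement, patient acceptance, and symptom occurrence between HD treatments will be performed using generalized estimating equations".

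On masking, section 10.6.1 states that "patients will not be informed of the treatment paradigm" and that "Investigators, including those performing TTE interpretation, will be blinded to treatment paradigm". Section 4.1 says the same and, like 10.6.1, adds: "Ultrasonographers performing intra-HD TTEs will be blinded to treatment paradigm". No other role is named there. Section 10.6.2 plans a check of blinding in participants only.

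On who may come to know the arm:
- Section 7.1.1 has clinic nursing staff set the UF profile on the machine.
- Section 9 says: "The PI and research Study Coordinator will conduct on-site monitoring (at least once per study phase) and centralized monitoring (every study treatment"; verifying adherence to the protocol is one stated purpose.
- Section 10.4.5 gives the same two people a weekly review of adherence.
- Section 8.6 states that the PI is blinded. The coordinator's status is not given anywhere.

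Section 5.3 and the fourth sensitivity analysis in the SAP show that the two treatments alternate over the four phases.

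**The concern.** The acceptance question asks for an opinion, and it is put face to face in the clinic. If the person asking knows the arm and has a view of it, tone or prompting can affect the answer. Blinding the patient protects against the patient's own expectation but not against the asker's.

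Such an effect, if it ran in a consistent direction, would sit entirely within the treatment contrast. Asking twice per treatment would not average it out. Neither the generalized estimating equations in protocol 10.4.3 nor the random-intercept logistic model in the SAP could separate it from a real difference in acceptance. With no check of staff blinding, it would also leave no trace. At stake is the reading of one secondary endpoint, which bears on whether patients would take up the intervention.

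**Working it through.** No figure in the plan bears on this point, so there is none to reproduce. The check is mainly a comparison of passages.

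**1. Whose masking is stated?**

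| Role | Masking | Source (protocol) |
|---|---|---|
| Patient | Blinded | 4.1, 10.6.1 |
| Investigators, including echo readers | Blinded | 4.1, 10.6.1; PI also in 8.6 |
| Sonographers | Blinded | 4.1, 10.6.1 |
| Clinic nurses | Not stated; they set the profile, so they know the arm | 7.1.1 |
| Study coordinator | Not stated; monitors adherence every treatment and weekly | 9, 10.4.5 |
| Staff who ask the acceptance question | Not stated; role not identified | 7.2.2 |

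Nothing in the protocol or SAP requires the asker to be unaware of the arm.

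**2. How much does one phase reveal?** With U for UF profiling and C for conventional, the two sequences are U-C-U-C and C-U-C-U. They differ in every phase, so the arm in any one phase identifies the sequence and hence all four arms. One lapse in masking is enough for that participant.

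**3. Scale, as an illustration only.** Inputs: 30 completers (5.3), and one answer per phase with two phases per treatment (4.2.2, 4.1).

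- Answers per treatment: 30 × 2 = 60. In total: 30 × 4 = 120.
- If the way of asking changed 1 in 20, 1 in 10 or 1 in 5 answers in one arm, all in one direction, the spurious difference would be 3/60 = 5 points, 6/60 = 10 points or 12/60 = 20 points. These rates are assumed.

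**4. Chance of a false significant result under assumed values.** Take a true difference of zero, two-sided 0.05 (10.4.1), baseline acceptance p between 50% and 80% (assumed), and an asker-induced shift s in one arm. Answers are treated as independent, with n per arm:

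Φ[(s − 1.96·SE0)/SE1], where SE0 = √(2·m(1−m)/n), m = p + s/2, and SE1 = √([p(1−p) + (p+s)(1−p−s)]/n).

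Worked case, p = 0.50, s = 0.10, n = 60: SE0 = √(2 × 0.55 × 0.45/60) = 0.0908; SE1 = √((0.25 + 0.24)/60) = 0.0904; (0.10 − 0.178)/0.0904 = −0.863; Φ = 0.194.

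| Shift | n = 60 per arm | n = 30 per arm |
|---|---|---|
| 5 points | 8% to 11% | 6% to 7% |
| 10 points | 19% to 33% | 12% to 19% |
| 15 points | 38% to 71% | 21% to 42% |

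The nominal chance in that direction is 2.5%. The n = 30 column stands for the case where a participant's two answers on the same treatment carry no more information than one. Both columns ignore the pairing of arms within participants. The table shows what a shift of a given size would do; it is no evidence that a shift exists.

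**The case against.** The case against has real force, and several stronger readings that a reader might infer do not survive it.

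- **That the coordinator asks the question.** Section 7.2.2 says only study staff. The coordinator may be among them, but no section says so.
- **That adherence monitoring means knowing the arm.** Sections 9 and 10.4.5 speak of adherence in general and share the task with a PI whom 8.6 declares blinded. On the plan's own terms, monitoring and blinding are meant to coexist. Seeing the arm is a plausible consequence of the check, not a stated one.
- **That study staff as a group are unblinded.** Section 13.3.2 counts the PI among study staff, so the term covers at least one blinded person. The accurate description is that masking is unspecified.
- **That chairside readings reveal the arm.** The hematocrit readings at the plasma refill test (7.2.2) are taken in both arms, and nothing says that they show which arm is running.
- **That a bias is present and always favors one arm.** The documents do not show that staff share an expectation or convey it. The patient is blinded, answers personally, and hears fixed wording that names no arm.

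It can also be said that this is one of seven secondary endpoints in a self-described pilot, with no power claim attached. That is fair, and it limits the priority of the point. What remains is that nothing in the plan masks the asker of a subjective question, although the plan already uses self-completion for symptoms.

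**Conclusion.** The point holds as a gap in the masking plan for one secondary endpoint. The person who elicits patient acceptance is not identified, that person's masking is not stated, and the alternating design means that one disclosure reveals the whole sequence. Influence on the answer is possible; the documents do not show that it would occur. Its size cannot be estimated from them: the 5 to 20 points and the probabilities above follow from assumed change rates and assumed baseline acceptance.

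This is a cheap improvement rather than a threat to the trial. It does not touch the three primary endpoints. The symptom form is also handed out by study staff but is less exposed, because patients fill it in themselves.

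**What to change.** In section 7.2.2, replace the oral question with self-completion:

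*At the end of treatment 9 of each phase, the participant marks the answer to the acceptance question, in the same wording and in English or Spanish, on a self-completed form like that in Appendix B, and places it in an envelope that is opened at data entry. If help with reading is needed, the text is read verbatim by a person unaware of the treatment arm, such as the clinic interpreter, and not by staff who set the UF profile or check adherence.*

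The requirement that the reader be unaware of the arm is essential. Excluding only those who check adherence would still admit clinic nurses, who set the profile.

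Cost: one printed line and one envelope per participant per phase, with no added visits or staff. The drawback is that a few blank answers may be noticed only at data entry, which matters somewhat with four answers per participant.

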7.2.3 SPECIMEN PREPARATION, HANDLING, AND STORAGE

Blood samples for Troponin T measurement will be collected via the vascular access by HD staff. Samples will be transported (on the day they are drawn by study staff) on ice for aliquoting and storage at -80°C in UNC Kidney Center freezers. Baseline blood (electrolytes, albumin, complete blood count, Kt/V, iron stores, bone-mineral tests) and 24-hour urine samples are being collected as part of routine care processes and will be processed per usual clinical procedures at an accredited laboratory.

7.2.4 SPECIMEN SHIPMENT

After aliquoting and transporting to UNC, Troponin T samples will be shipped to an accredited laboratory for testing per usual clinical procedures.

7.3 STUDY SCHEDULE

7.3.1 SCREENING

The PI will communicate with potential participants to determine whether they fit the inclusion/exclusion criteria and would like to participate in the study. If patients are interested in participating, a signed HIPAA waiver will be obtained to allow the PI to review the individual's medical record and confirm eligibility status. The study baseline period will begin within 4 weeks of enrollment.

7.3.2 ENROLLMENT/BASELINE

Written informed consent will be obtained from study subjects prior to the implementation of any study procedures. The subject will receive a signed and dated informed consent form. The PI will verify inclusion/exclusion criteria. A complete medical history, physical examination and baseline TTE will be taken at the time of enrollment (baseline).

7.3.3 FOLLOW-UP

All study visits will occur at the time of routinely scheduled dialysis treatments at the patient's usual outpatient dialysis clinic. Monitoring and recording of BP and weights will be performed at every treatment. See "7.3.7 Schedule of Events Table" for planned frequency of additional monitoring and testing.

7.3.4 FINAL STUDY VISIT

N/A (the final study visit is no different than the follow-up visits).

7.3.7 SCHEDULE OF EVENTS TABLE

Procedures	Baseline (6 week prior to study start)	Every study HD treatment	Before and after 7 th HD treatment of each phase	During 7 th HD treatment of each phase (twice per treatment type)	During 7 th HD treatment in the first phase of each treatment type (once per treatment type)	After 9 th HD treatment of each phase	After 1st HD treatment of each week (3x/phase)
Baseline laboratory testing	X						
Baseline history and physical	X						
Pregnancy status inquiry	X						
BP monitoring	X	X					
Weight monitoring	X	X					
Blood volume monitoring	X					X	
Troponin T laboratory testing			X				
TTE	X				X		
Plasma refill test	X			X			
Patient acceptance assessment						X	
Symptoms assessment						X	

7.4 JUSTIFICATION FOR SENSITIVE PROCEDURES

N/A

7.5 CONCOMITANT MEDICATIONS, TREATMENTS, AND PROCEDURES

There will be no change to a patient's usual medications or dialysis treatments (other than UF profiling during UF profiled arms).

7.5.1 PRECAUTIONARY MEDICATIONS, TREATMENTS, AND PROCEDURES

N/A

7.6 PROHIBITED MEDICATIONS, TREATMENTS, AND PROCEDURES

N/A

7.7 PROPHYLACTIC MEDICATIONS, TREATMENTS, AND PROCEDURES

N/A

7.8 RESCUE MEDICATIONS, TREATMENTS, AND PROCEDURES

Any hemodynamic instability experienced during study HD will be managed per routine protocols with standard interventions (e.g. saline administration, reduction in UF rate or blood flow).

7.9 PARTICIPANT ACCESS TO STUDY AGENT AT STUDY CLOSURE

Participants will have access to UF profiling during HD treatments at study closure if deemed appropriate by their treating nephrologists.

